7.6.8.3 Time-to resolution of other events of special interest

See Core Safety SAP.

- Time-to resolution of any grade other events of special interest
- Time-to resolution of grade 3 to 5 other events of special interest
- Time-to resolution of any grade drug-related other events of special interest
- Time-to resolution of grade 3 to 5 drug-related other events of special interest
- Time-to resolution of any grade other events of special interest where immune modulating medication was initiated
- Time-to resolution of grade 3 to 5 other events of special interest where immune modulating medication was initiated

Time-to resolution analyses will be restricted to treated subjects who experience the other events of special interest. Time-to resolution where immune modulating medication is initiated analyses

will be restricted to treated subjects who experience the other events of special interest and who receive immune modulating medication during the longest other events of special interest.

The following summary statistics will be reported: percentage of subjects who experienced the other events of special interest, percentage of subjects with resolution of their other events of special interest of longest duration, median time-to resolution (derived from Kaplan-Meier estimation) and ranges.

See time-to resolution definition subsection of [APPENDIX 1](#) for additional details.

The analyses will be conducted using the 100-day safety window.

7.6.9 Immune modulating medication

The percentage of subjects who receive immune modulating concomitant medication for

- management of adverse event
- other use

will be reported separately for each treatment arm (percentages of treated subjects by medication class and generic term).

Management of select AEs

For each category/subcategory of select AEs (see [Table 11-2](#)), the following will be reported for each treatment arm:

- Percentage of subjects who received immune modulating concomitant medication for management of any select AE in the category among subjects who experienced at least one select adverse event in the category/subcategory.
- The total duration of immune modulating concomitant medication for select adverse event management.

These analyses will be performed on any select AEs, drug-related select AEs, select endocrine AEs and drug-related select endocrine AEs.

The analysis will be conducted using the 30-day safety window.

Management of IMAEs

For each category of IMAEs, the following will be reported for each treatment arm:

- Percentage of subjects who receive immune modulating concomitant medication for management of IMAE in the category among subjects who experience at least one IMAE in the category.
- The total duration of immune modulating concomitant medication for IMAE management.

The analysis will be conducted using the 100-day safety window.

Management of other events of special interest

For each category of other events of special interest, the following will be reported for each treatment arm:

- Percentage of subjects who receive immune modulating concomitant medication for management of other events of special interest in the category among subjects who experience at least one other event of special interest in the category.
- The total duration of immune modulating concomitant medication for other events of special interest management.

The analyses will be conducted using the 100-day safety window.

7.6.10 Multiple Events

The following summary tables will be provided for all treated subjects by treatment arms:

- A table showing the total number and rate (exposure adjusted) of occurrences of all AEs.
- A table showing the total number and rate (exposure adjusted) of occurrences for all AEs with an incidence at least 5% in any treatment arm.

In addition, the rate (exposure adjusted) and its 95% CI evaluated for different time intervals will be displayed graphically for each treatment group. This analysis will be limited to the rate of all AEs and all drug-related AEs.

The analyses will be conducted using the 30-day safety window and repeated using the 100-day safety window.

For select AEs:

- A table showing the number of subjects experiencing an AE once or multiple times in each treatment arm

The analyses will be conducted using the 30-day safety window.

A Listing displaying the unique instances of all AEs, i.e., after duplicates have been eliminated and overlapping and contiguous occurrences of the same event (i.e. same PT) have been collapsed will be provided.

7.6.11 Clinical laboratory evaluations

The analysis population for each laboratory test is restricted to treated subjects who undergo that laboratory test.

7.6.11.1 Hematology

See Core Safety SAP.

7.6.11.2 Serum Chemistry

See Core Safety SAP

7.6.11.3 Electrolytes

See Core Safety SAP.

7.6.11.4 Additional Analyses

See Core Safety SAP.

7.6.12 Vital Signs and Pulse Oximetry

See Core Safety SAP

7.6.13 Immunogenicity Analysis

Definitions and analyses of immunogenicity are described in the core/integrated SAP for immunogenicity data of nivolumab document.

7.6.14 Pregnancy

See Core Safety SAP.

7.6.15 Clinical Safety Program (CSP)

Not applicable.

7.6.16 Adverse Events By Subgroup

Overall summary of drug-related AEs, drug-related serious AEs, and drug-related AEs leading to discontinuation by worst CTC grade (any grade, grade 3-4, grade 5) will be presented by SOC/PT and for each treatment arm for the following subgroups using the 100-day safety window:

- Gender (male vs. female)
- Age categorization (< 65 vs. ≥ 65)
- Baseline ECOG PS (0, 1, 2)
- Line of prior therapy (first line vs. ≥ second line)

An overall summary of immune modulating AEs by worst CTC grade (grade 1, 2, 3, 4, 5) will be presented by immune mediated category/PT and for each treatment arm for the above subgroups using the 100-day safety window.

In addition to the above subgroup analyses, a summary of serious AEs by worst CTC grade (any grade, grade 3-4, grade 5) and a summary of immune modulating AEs by worst CTC grade (grade 1, 2, 3, 4, 5) will be presented for the subgroups defined by duration of prior Nivolumab treatment (< 3 months, 3 - < 6 months vs. ≥ 6 months).

[Redacted text block]

[REDACTED]

[REDACTED]

[REDACTED]

[REDACTED]

7.10 Interim Analyses

The first safety interim analysis will be conducted after 25 subjects per treatment arm with at least 3 months of treatment exposure after randomization. It is anticipated that the DMC will meet at every 6 months to perform safety assessments.

In addition to the interim analyses specified above, additional interim analyses might be conducted, for example, to address regulatory questions or requests.

8 CONVENTIONS

The following conventions may be used for imputing partial dates for analyses requiring dates:

- For missing and partial AE onset dates, imputation will be performed using the Adverse Event Domain Requirements Specification.
- For missing and partial AE resolution dates, imputation will be performed as follows:
 - If only the day of the month is missing, the last day of the month will be used to replace the missing day
 - If the day and month are missing or a date is completely missing, it will be considered as missing.
- Missing and partial non-study medication domain dates will be imputed using the derivation algorithm described in Section 4.3.3 of BMS Non-Study Medication Domain Requirements Specification.

For death dates, the following conventions will be used for imputing partial dates:

- If only the day of the month is missing, the 1st of the month will be used to replace the missing day. The imputed date will be compared to the last known date alive + 1 day and the maximum will be considered as the death date.
- If the month or the year is missing, the death date will be imputed as the last known date alive + 1 day.
- If the date is completely missing but the reason for death is present the death date will be imputed as the last known date alive + 1 day

For the date of progression, the following conventions will be used for imputing partial dates:

- If only the day of the month is missing, the 1st of the month will be used to replace the missing day*.
- If the day and month are missing or a date is completely missing, it will be considered as missing.

* In the case of the date of death being present and complete, the imputed progression date will be compared to the date of death. The minimum of the imputed progression date and date of death will be considered as the date of progression.

For other partial/missing dates, the following conventions will be used:

- If only the day of the month is missing, the 15th of the month will be used to replace the missing day.
- If both the day and the month are missing, “July 1” will be used to replace the missing information.
- If a date is completely missing, it will be considered as missing.

The following conversion factors will be used to convert days to months or years: 1 month = 30.4375 days and 1 year = 365.25 days.

Duration (e.g. time from first diagnosis of NSCLC to randomization, time-to onset, time-to resolution) will be calculated as follows:

Duration = (Last date - first date + 1)

Last known date alive will be defined based on all appropriate dates collected on the CRF.

All statistical analyses will be carried out using SAS (Statistical Analysis System software, SAS Institute, North Carolina, USA) unless otherwise noted.

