In order to derive the time-to resolution, overlapping or contiguous select AEs within a specific category (defined in [Table 11-2](#)) will be collapsed into what will be termed “clustered” select AEs. For example, if a subject (without pre-treatment AE) experienced an AE from 1st to 5th January, another AE (with different PT but within same category) from 6th to 11th January and same AE from 10th to 12th January, these will be collapsed into one clustered select AE from 1st to 12th January. [Table 11-1](#) is summarizing key derivation steps for each type of clustered select AEs.

Time-to resolution of select AE (any grade) for a specific category is defined as the longest time from onset to complete resolution or improvement to the grade at baseline among all clustered select AEs in this category experienced by the subject. Events which worsen into grade 5 events (death) or have a resolution date equal to the date of death will be considered unresolved. If a

clustered select AE is considered as unresolved, the resolution date will be censored to the last known date alive. Improvement to the grade at baseline implies that all different AE events in the clustered select adverse event should at least have improved to the corresponding (i.e. with same preferred term) baseline grade. This measure is defined only for subjects who experienced at least one select AE in the specific category.

The time-to resolution of select AE (grade 3-5) for a specific category is defined similarly with an onset date corresponding to a grade 3-5 select AE.

Time-to resolution of drug-related select AE (any grade or grade 3-5) is defined similarly but restricted to drug-related select AE.

The time-to resolution of select AE (any grade or grade 3-5, drug-related or all) where immune modulating medication is initiated is defined similarly with the additional condition that the subject started an immune modulating medication during the longest select AE resolution period.

Time-to resolution for a specific subcategory is defined similarly but restricted to event of this subcategory.

Table 11-1: Derivation of clustered select AE

Type of clustered select AE	Derivation
Any grade	Collapse any on-treatment select AE from the same category
Drug-related of any grade	Collapse any on-treatment drug-related select AE from the same category

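### A non-fatal AE with a month-only end date in the month of death is imputed to month-end with no cap at death, so it escapes the at-death rule and counts as resolved after death

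*SAP*

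**What the plan says.** SAP Section 8 gives separate rules for partial dates.

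- **AE resolution date, day missing:** "If only the day of the month is missing, the last day of the month will be used to replace the missing day". No comparison with death or last known date alive follows.
- **AE resolution date, more than the day missing:** "If the day and month are missing or a date is completely missing, it will be considered as missing".
- **Death date, day missing:** the 1st of the month is used, and then "The imputed date will be compared to the last known date alive + 1 day and the maximum will be considered as the death date".
- **Progression date, day missing:** the 1st of the month is used and, where a complete death date exists, "The minimum of the imputed progression date and date of death will be considered as the date of progression".

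SAP Appendix 1 (time-to resolution definition) sets the status. "Events which worsen into grade 5 events (death) or have a resolution date equal to the date of death" are treated as unresolved, and for an unresolved cluster "the resolution date will be censored to the last known date alive". There is no rule for a resolution date later than death.

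Sections 7.6.6.3, 7.6.7.3 and 7.6.8.3 all refer to Appendix 1 for time to resolution. They report the percentage of subjects whose longest event resolved, the Kaplan-Meier median and the range.

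**The concern.** The at-death rule exists so that an event which stopped only because the subject died is not scored as a resolution. It depends on an exact date match. The imputation rule moves a month-only end date to month-end, which nearly always breaks that match when the month is the month of death. The event then passes as resolved on a date when the subject was already dead.

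The progression-date rule in the same section has a cap at death, so the hazard was handled for one kind of date and left open for the other. When the day of death is also missing, the two imputation rules pull in opposite directions: death goes toward the start of the month and AE resolution to the end.

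At stake are the percentage resolved and the time-to-resolution summaries. Because Appendix 1 keeps each subject's longest cluster, an end date stretched past death is also more likely to belong to the cluster that is analysed.

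**Working it through.** The plan states no figure for this rule, so there is nothing to reproduce. The check applies the rules to dates.

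**Conditions for the problem.** All must hold: the event is not Grade 5; a resolution month is recorded; the day is missing; and the month is the month of death. An event with no end date, or with day and month missing, stays missing. A Grade 5 event is unresolved whatever its date. A complete end date equal to the death date is handled as intended.

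**How often the dates match.** Assume a complete death date and deaths spread evenly over a 365-day year.

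- The imputed date equals the death date only on the 12 month-ends: 12/365 = 3.3%.
- On the other 365 − 12 = 353 days (353/365 = 96.7%) it falls after death.
- Overshoot per day is month length minus day of month, and its total over a month of length L is L(L − 1)/2. Over the year: 7 × 465 + 4 × 435 + 378 = 5,373 days.
- Mean overshoot when it occurs: 5,373/353 = 15.2 days, range 1 to 30.

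**Example 1 (assumed dates).** Onset 1 March, death 10 March, last known alive 9 March, resolution recorded as March with no day.

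| Rule | End date | Status | Duration |
|---|---|---|---|
| As written | 31 March | Resolved, 31 − 10 = 21 days after death | 31 − 1 + 1 = 31 days |
| Capped at death | 10 March, equal to death | Unresolved, censored 9 March | 9 − 1 + 1 = 9 days |

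**Example 2 (assumed dates), day of death also missing.** Last known alive 20 May; death and AE resolution both recorded as June.

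- Death: the later of 1 June and 21 May, so 1 June.
- AE resolution: 30 June, which is 29 days after the imputed death, so resolved.
- With a cap at the imputed death date: 1 June, equal to death, so unresolved.
- With a cap at last known date alive: 20 May, which precedes death. The event is resolved again, in a month earlier than the one recorded.

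Example 2 shows why last known date alive is the wrong cap for subjects who died. An imputed death date is never earlier than last known date alive plus one day, so that cap would put the end date before death and the event would pass any at-death test.

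**Leverage of one subject.** Category counts can be small. Protocol Table 1.4.2-1 (CA209017, 131 nivolumab subjects, all causality) lists 3 with hepatic, 7 with pulmonary and 7 with renal select AEs. One subject in 7 moves percent resolved by 1/7 = 14 points. This only illustrates scale: that trial enrolled a different population, and a misdated event changes the result only if it lies in, or creates, the subject's longest cluster.

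**The case against.** The strongest case against the point has four parts.

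1. **Narrow scope.** A reader might infer that AEs still present at death are in general counted as resolved. The documents do not support that. Events with no end date, with only a year, of Grade 5, or with a full end date equal to death are all outside the problem. Nothing shows that sites give a month-only end date to an event ongoing at death. This stands, and the point is limited accordingly.
2. **The 96.7% is not an error rate.** A reader might take it as the share of AEs misclassified in this trial. It is calendar arithmetic, conditional on the event already meeting every condition above. Some such events may truly have resolved earlier in the month; for those the status is right and only the date is impossible. This also stands.
3. **Other documents may close the gap.** The three time-to-resolution sections open by referring to the Core Safety SAP, and Section 8 says only that its conventions may be used. A cap could exist in the Core Safety SAP or a domain specification. That cannot be ruled out. But neither Section 8 nor Appendix 1 contains or points to one for AE resolution dates.
4. **Small consequence.** Only descriptive safety summaries are touched. This is true, and it sets the priority, but the rules as written still allow a resolution date after death.

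**Conclusion.** The point holds within its limits. For a non-Grade-5 AE with a month-only resolution date in the month of death, Section 8 and Appendix 1 together count the event as resolved 1 to 30 days after death, unless death fell on the last day of the month. The direction is toward a higher percentage resolved; durations can also run past death.

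The number of subjects affected cannot be derived, because the documents do not say how often end days are missing; that it is small is a judgement. PFS, OS and AE incidence do not depend on this rule. The conclusion assumes that Section 8 is applied as written and that no cap exists in the Core Safety SAP or the domain specifications. It is a minor defect, worth correcting because correction is nearly free.

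**What to change.** 1. **SAP Section 8, AE resolution dates.** For subjects who died, take the earlier of the imputed resolution date and the date of death, using the imputed death date where the recorded one is partial. This follows the cap already in place for progression dates. Do not cap at last known date alive for these subjects.
2. **SAP Appendix 1.** Change the at-death test from a resolution date that equals the date of death to one that is on or after it.
3. **Core Safety SAP.** Check whether it already has a cap; if so, cite it in Section 8 and align the wording.

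For the partial dates discussed here, either of the first two edits alone would correct the status. Together they also keep impossible dates out of the clusters and listings.

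The cost is two phrases and one programming condition, with no new data. There is one small downside: an AE that truly resolved earlier in the month of death, but has a month-only end date, will be treated as unresolved and censored.

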**Table 5.1-3: Off-Treatment Follow-Up Assessments (CA209384)**

Procedure	Follow-up Visits 1 (XO1) and 2 (XO2) XO1 to occur approximately 30 days ± 5 days after last dose or coinciding with the date of discontinuation if the date of discontinuation (± 5 days) is greater than 35 days after the last dose. XO2 to occur approximately 70 days after XO1 (± 5 days)	Further Follow-Up Every 6 months (±1 month) after Follow-Up Visit 2 for up to 3 years	Notes
Outcomes Assessments			
EQ-5D-3L	X	X	Can be conducted via a telephone call if an in-person clinical visit is not otherwise needed.

ALT, alanine aminotransferase; ALP, alkaline phosphatase; ANC, absolute neutrophil count; AST, aspartate aminotransferase; BP, blood pressure; CTCAE, Common Terminology Criteria for Adverse Events; HR, heart rate; RR respiratory rate; NCI, National Cancer Institute; O2, oxygen; TSH, thyroid stimulating hormone; WBC, white blood count; WOCBP, women of childbearing potential.

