4 ENDPOINTS

4.1 Primary Endpoints

The coprimary endpoints of this trial will be assessed by PFS rate at 6 months after randomization and PFS rate at 1 year after randomization. PFS is defined as the time from the date of randomization to the date of first documented tumor progression determined by the investigator using RECIST 1.1 criteria or death due to any cause, whichever is earlier. Subjects who do not progress or die will be censored on the date of their last evaluable tumor assessment. Clinical deterioration in the absence of unequivocal evidence of progression (per RECIST 1.1) is not considered progression for purposes of determining PFS. Subjects who die without a reported prior progression will be considered to have progressed on the date of their death. Subjects who do not have any on-study tumor assessments and do not die will be censored on the date of randomization. Subjects who receive any subsequent anti-cancer therapy (including on-treatment palliative radio therapy [RT] of non-target bone lesions or central nervous system [CNS] lesions) without a prior reported progression will be censored at the last evaluable tumor assessment prior to or on the date of initiation of the subsequent anti-cancer therapy.

Table 4.1-1: Censoring Scheme for Primary Definition of PFS

Situation	Date of Progression or Censoring	Outcome
No baseline tumor assessments and no death	Randomization	Censored
No on study tumor assessments and no death	Randomization	Censored
New anticancer treatment started without a prior reported progression per RECIST 1.1 or death	Date of last evaluable tumor assessment prior to or on the date of initiation of the subsequent anti-cancer therapy	Censored
Progression per RECIST 1.1 documented at scheduled or unscheduled visit and no new anticancer treatment started before	Date of the first documented tumor progression	Progressed
Subject progression free (per RECIST 1.1) and no new anticancer treatment started	Date of last tumor assessment	Censored
Death without prior progression per RECIST 1.1 and no new anticancer treatment started	Date of death	Progressed

RECIST: Response Evaluation Criteria in Solid Tumors

[figure not shown]
PFS rate at 6 months is the rate from Kaplan-Meier estimate 6 months after randomization; PFS rate at 1 year is the rate from Kaplan-Meier estimate at 1 year after randomization.

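### The SAP's rule for a death with a missing month ignores a recorded year, so an imputed death can fall in a year before the recorded one; the rule for partial radiotherapy dates is not named

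*SAP*

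**What the plan says.** **Death dates (SAP Section 8).** When only the day is missing, the first of the recorded month is imputed, and then: "The imputed date will be compared to the last known date alive + 1 day and the maximum" of the two is the death date. The next bullet reads: "If the month or the year is missing, the death date will be imputed as the last known date alive + 1 day". It makes no comparison with a recorded year. The anchor is broad: "Last known date alive will be defined based on all appropriate dates collected on the CRF".

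**Where death dates are used.** SAP 7.5.2 plans OS rates at 6, 12, 18, 24 and 36 months. SAP 4.1 counts a death without earlier progression or new therapy as a PFS event on its date.

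**Other dates (SAP Section 8).** For dates with no rule of their own: "If only the day of the month is missing, the 15th of the month will be used to replace the missing day", and "If both the day and the month are missing, “July 1” will be used to replace the missing information". Drug dates are handled elsewhere: "Missing and partial non-study medication domain dates will be imputed using the derivation algorithm described in Section 4.3.3" of a sponsor specification that is not part of the documents. No rule is named for subsequent radiotherapy.

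**PFS censoring (SAP 4.1, Table 4.1-1).** The situation "New anticancer treatment started without a prior reported progression per RECIST 1.1 or death" censors the subject at the last evaluable scan on or before the start of that treatment. Section 4.1 counts on-treatment palliative radiotherapy of non-target bone or CNS lesions as such treatment.

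**The concern.** A recorded year of death is information. A rule that ignores it can yield a date that the case report form itself rules out. When that happens the date is too early, never too late, so a death can be carried back across an OS milestone. The two neighbouring bullets also disagree in principle: one treats the known part of the date as a floor and the other does not.

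The radiotherapy question is of a different kind. Whether a progression counts as an event or as censoring depends on which came first, the progression or the new therapy. If a partial therapy date is filled with a calendar default and not compared with the progression date, that default decides the status of a co-primary event.

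**Working it through.** The plan gives no figure on this point to reproduce, so the check applies the rules literally to example dates. The dates are my assumptions.

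**1. The month-missing death rule.** SAP result = last known alive + 1 day. Bounded result = later of 1 January of the recorded year and last known alive + 1 day.

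| Last known alive | Death recorded as | SAP date | Bounded date | Difference |
|---|---|---|---|---|
| 15-Jun-2018 | 2019 | 16-Jun-2018 | 01-Jan-2019 | 199 days |
| 01-Oct-2018 | 2019 | 02-Oct-2018 | 01-Jan-2019 | 91 days |
| 10-Oct-2018 | 2019 | 11-Oct-2018 | 01-Jan-2019 | 82 days |
| 31-Dec-2018 | 2019 | 01-Jan-2019 | 01-Jan-2019 | 0 days |

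For contrast, take last known alive 10-Oct-2018 and death recorded as January 2019. The day-missing rule gives 01-Jan-2019. Both records exclude 2018, but only one rule respects that.

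**2. Crossing a milestone.** Randomization on 20-Dec-2017, last known alive 10-Oct-2018, death recorded as 2019. With the SAP's duration formula (last date − first date + 1, and 30.4375 days per month):
- SAP date: (295 + 1)/30.4375 = 9.7 months.
- Earliest date the record allows: (377 + 1)/30.4375 = 12.4 months.

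The death is counted before the 12-month OS milestone, although the recorded year places it after.

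**3. How large the shift can be.**
- *OS.* Protocol Table 5.1-3 has two follow-up visits, about 30 days and then about 30 + 70 = 100 days after the last dose. After that, contacts are 6 months apart with a 1-month window. A gap of about 6 + 1 = 7 months that spans a year end is therefore within schedule.
- *PFS.* A death enters PFS only if there was no earlier progression or new therapy. Such subjects are still scanned every 8 weeks (±1 week) in year 1 and every 3 months in year 2, even off treatment. The scheduled year-1 gap is about 8 + 1 = 9 weeks, or 63 days. The example in step 2 needs 82 days without contact, so for PFS it would take a missed scan.

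**4. Size for OS.** With about 350/2 = 175 per arm (SAP Section 5) and no earlier censoring, one death wrongly moved before a milestone lowers that arm's OS rate there by about 1/175 = 0.57 points.

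**5. Radiotherapy, if the default for other dates governs.**
- Progression 20-Mar-2018, radiotherapy recorded as March 2018: imputed 15-Mar, before progression, so censored.
- Progression 10-Mar-2018, same record: imputed 15-Mar, still an event.
- Progression 10-Sep-2018, radiotherapy recorded as 2018: imputed 01-Jul, so censored.
- Progression date also missing its day: set to the 1st, so the order is kept.

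Assume a uniform progression day and radiotherapy truly 1–7, 1–14 or 1–21 days later in the same month. Then about 42%, 33% or 26% of day-missing cases reverse order. With only the year recorded and a lag of 1–14 days, about 49% do.

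*Effect on the rate.* Assume 175 per arm, exponential PFS with 0.48 at 12 months, and an event near month 4 re-censored at month 2. Approximately, 0.48/(175 × 0.78) = 0.35 points. A direct Kaplan-Meier calculation gives 0.4831 − 0.4800 = 0.31 points for one subject, 1.0 for three, 1.6 for five and 3.3 for ten.

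**6. Against the precision of the estimate.** The one-sided 95% distance from the estimated difference to its lower bound at 12 months is about 1.645 × √(2 × 0.48 × 0.52/175) = 1.645 × 5.3 = 8.8 points.

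**The case against.** The strongest case is that this will hardly matter. The documents give no frequency of partial dates. Protocol 3.6.2 tells sites to obtain the date of death by permissible local methods, and Protocol 9.2.3 requires investigator review of the case report forms. Section 8 introduces its conventions as ones that may be applied. Formal non-inferiority testing has been dropped in favour of an interval, so no decision rule hangs on a fraction of a point. The off-treatment contact schedule is the same in both arms, so errors of similar frequency would largely cancel in the difference. All of this stands as a limit on size. None of it makes a date that contradicts the recorded year correct, and the death bullets are themselves worded as firm rules.

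On radiotherapy, the objection cuts deeper. A reader might infer that such dates certainly take the 15th or July 1 and that true PFS events will be lost. The SAP does not establish that. SAP 7.3.4 lists radiotherapy apart from non-study medication, but for prior therapy; SAP 7.4.4 groups it under subsequent therapy. If the external medication specification governs, the documents cannot show the outcome.

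Three further inferences also go too far:
- That each lost PFS event is worth 1/175, about 0.6 points. That treats the subject as event-free to the milestone, but the subject is censored.
- That the 7-month shift applies to the co-primary PFS rates. It belongs to late survival follow-up.
- That these rules run without review. The documents do not say so, and SAP 7.4.4 already plans a by-subject listing of subsequent therapy including radiotherapy.

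**Conclusion.** The death-date point holds and is minor. As written, the month-missing rule gives an impossible date whenever the year is recorded and last known alive + 1 day falls in an earlier year. The error is always early. It bears mainly on the OS rates, which are secondary, with shifts of up to about 7 months in late follow-up and about 0.57 points per death that crosses a milestone. Its reach into the co-primary PFS rates is limited by the scan schedule. The conclusion assumes that some deaths will be recorded with a year only; probably few.

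The radiotherapy point holds only conditionally. It requires that the default for other partial dates governs, that the progression date is complete, and that the imputed start falls before it. If so, each affected subject raises an arm's 12-month PFS rate by about 0.3 points, through censoring that is informative because the subject did progress. A progression after month 6 would not alter the 6-month rate. What the documents do show is a gap: the governing rule is not named.

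**What to change.** **Death dates.** Replace the bullet in SAP Section 8 so that, when the year of death is known and the month is missing, the death date is the later of 1 January of that year and last known date alive + 1 day. Keep the present rule only when the year is missing. This costs one sentence and a line of code.

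**Radiotherapy dates.** State which rule governs partial start dates of subsequent therapy, with radiotherapy named. Flag, within the listing already planned in SAP 7.4.4, the subjects whose event or censoring status depends on an imputed therapy date. Report the co-primary PFS rates under both orderings for them as a sensitivity analysis. This costs one or two sentences, a flag and one repeat analysis.

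I would not force same-month therapy to fall on or after progression. If radiotherapy truly began on the 5th and progression came on the 20th, the 15th correctly leads to censoring, and a forced ordering would wrongly make it an event. A same-month rule would also leave the July 1 default untouched in most cases. Neither change affects the design, data collection or conduct of the trial.
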